1.2 Study Rationale

1.2.1 Known and Potential Risks and Benefits to Subjects/Patients

Rucaparib has demonstrated clinical benefit in patients with deleterious mutations in HRR genes in a variety of tumor types as described previously ([Section 1.1.4](#)) and is approved for EOC, FTC and PPC, and mCRPC ([Section 1.1.6](#)).

The benefit:risk ratio of rucaparib is described in detail in the IB.

1.2.2 Rationale for the Study Design

This study is designed to test the effectiveness of rucaparib across a range of solid tumor types, including more prevalent types (eg, breast cancer) as well as rarer tumor types (eg, sarcoma). Patients will be required to have deleterious mutations in certain HRR genes hypothesized to drive responsiveness to rucaparib. The drug is intended to be tested in second-line onwards, while restricting pretreatment to 3 chemotherapy treatment lines in most instances. A futility analysis is planned for each tumor type, to identify tumor types that may be inherently non-responsive to rucaparib, (perhaps due to deleterious mutations in HRR genes not being driver mutations in those tumors, or a high rate of reversion mutations). There is no comparator arm in this study, as the study incorporates a variety of tumor types with vastly different treatment paradigms. The study is expected to enroll a wide variety of tumor types, thereby providing support for a tumor-agnostic indication for rucaparib.

1.2.3 Dose Rationale

Rucaparib will be dosed at 600 mg BID as the starting dose, the approved dose for ovarian cancer indications and also the dose used in a variety of ongoing trials. More supportive evidence for this dose is found in the IB.

1.2.4 Rationale for Duration of Treatment

Patients will be treated as long as they tolerate the drug well, do not progress and do not withdraw consent to be in the trial, since the goal of the trial is to assess rucaparib safety and efficacy in various tumor types.

2 STUDY OBJECTIVES AND ENDPOINTS

Primary, secondary, and exploratory objectives and endpoints are shown in [Table 1](#).

Table 1. Study Objectives and Endpoints

Objectives	Endpoints	Justifications
Primary Objective	Primary Endpoint	Justification for Primary Endpoint

To determine the ORR by tumor type, as assessed by the investigator, to be evaluated by RECIST v1.1 (or by RECIST v1.1 and Prostate Cancer Working Group Guidelines Version 3 [PCWG3] in patients with mCRPC).
	
Best overall response as assessed by the investigator by RECIST v1.1 (or by RECIST v1.1 and PCWG3 in patients with mCRPC).
	
Best overall response is summarized across patients as ORR, which is the proportion of complete responses and partial responses confirmed in patients with measurable disease and is a direct measure of the drug’s anti-tumor activity. It is commonly used in Phase 2 trials. It excludes stable disease, which may be more reflective of the natural history of the disease rather than response to the investigational drug.

Secondary Objectives	Secondary Endpoints	Justifications for Secondary Endpoints

1. To assess ORR by independent radiology review (IRR).
	
1. ORR as assessed by IRR (irrORR) by RECIST v1.1 (or by RECIST v1.1 and PCWG3 in patients with mCRPC).
	
1. Best overall response as assessed by IRR is summarized across patients as irrORR, which provides a measure of ORR that is devoid of the heterogeneity arising from radiology data being evaluated at various investigational sites and serves as a more independent evaluation of ORR.

2. To assess the duration of response (DOR).
	
2. DOR
	
2. DOR, defined as the time from initial tumor response to documented tumor progression, provides additional information on the longevity of tumor response.

Table 1. Study Objectives and Endpoints

Objectives	Endpoints	Justifications
3. To evaluate DCR.	3. DCR	3. DCR, defined as the percentage of complete response (CR), PR, and stable disease (SD) beyond 16 weeks, is another measure of clinical benefit to the investigational drug, being a composite of SD and ORR.
4. To estimate progression-free survival (PFS).	4. PFS	4. Defined as the duration from entry into study to objective tumor progression or death of a patient, PFS is a measure of clinical benefit.
5. To estimate OS.	5. OS	5. Defined as the duration from entry into study to death, OS is the gold standard for oncology clinical trials.
6. To evaluate the safety and tolerability of rucaparib.	6. Incidence of adverse events, clinical laboratory abnormalities and dose modifications.	6. In accordance with International Council for Harmonisation (ICH) E9 principles, acute and long-term evaluation of medical risks including adverse events (AEs), laboratory tests, vital signs and other special safety tests (eg, ECGs) will be assessed.
7. To evaluate steady-state PK of rucaparib.	7. Steady-state minimum concentration (C_{min}).	7. Sparse PK allows for monitoring of rucaparib exposure in various cancer types and exploratory exposure response analysis.

Table 1. Study Objectives and Endpoints

Objectives	Endpoints	Justifications

Exploratory Objectives
 
1. To assess resistance mutations detected in circulating tumor DNA (ctDNA).
 
2. To evaluate zygosity of deleterious mutations detected in HRR genes within tumor tissue.
	
Exploratory Endpoints
 
1. Best overall response, DOR and PFS summarized in patients with and without resistance mutations in ctDNA.
 
2. Best overall response, DOR and PFS summarized in patients with homozygous vs heterozygous mutations in HRR genes.
	
Justification for Exploratory Endpoints
 
1. Primary and acquired resistance mutations to rucaparib have been identified in ctDNA from ovarian and prostate cancer patients. This objective will evaluate if these resistance mutations have an impact on rucaparib clinical efficacy across tumor types.
 
2. HRD typically results from biallelic inactivation of an HRR gene. This exploratory objective will evaluate if patients with homozygous mutations in HRR genes derive greater rucaparib clinical efficacy.

Abbreviations: AE = adverse event; C_{min} = steady-state minimum concentration; CR = complete response; ctDNA = circulating tumor DNA; DCR = disease control rate; DNA = deoxyribonucleic acid; DOR = duration of response; ECG = electrocardiogram; HRD = homologous recombination deficiency; HRR = homologous recombination repair; ICH = International Council for Harmonisation; IRR = independent radiology review; irrORR = objective response rate as assessed by independent radiology review; mCRPC = metastatic castration-resistant prostate cancer; ORR = objective response rate; OS = overall survival; PCWG3 = Prostate Cancer Working Group Guidelines Version 3; PFS = progression-free survival; PK = pharmacokinetics; PR = partial response; RECIST v1.1 = Response Evaluation Criteria in Solid Tumors Version 1.1; SD = stable disease.

3 STUDY DESIGN

3.1 Overall Study Design

This study is a Phase 2, open-label, single arm trial designed to evaluate the response to rucaparib of patients with various solid tumors and with deleterious mutations in HRR genes, including the following: BRCA1, BRCA2, PALB2, RAD51C or RAD51D (comprising Cohort A). Patients with deleterious mutations in BARD1, BRIP1, FANCA, NBN, RAD51 and RAD51B may also enroll into an exploratory cohort (Cohort B). Since the trial is designed to test rucaparib responsiveness across a range of tumor types (tumor-agnostic indication), patients with rare tumor types with these mutations, eg, leiomyosarcoma or uterine carcinosarcoma, are equally eligible, in addition to the high prevalence tumor types such as breast, prostate and lung cancer. Patients may be grouped by tumor types, that may range in size from as few as a single patient (for rare tumor types) to an upper limit described below.

The study incorporates a futility analysis; if there are at least 11 patients of a particular tumor type enrolled into the study without a response, enrollment of additional patients with that tumor may be discontinued. In addition, the study incorporates an upper limit of 50 patients of a particular tumor type; however, this limit may be removed if the benefit-risk ratio of the drug is deemed to be favorable for patients.

3.1.1 Screening Period

All patients will undergo screening assessments up to 4 weeks prior to enrollment.

Screening assessments will include, but may not be limited to, demographics and medical history, prior cancer treatments, prior and current medications and procedures, 12-lead ECG, Eastern Cooperative Oncology Group (ECOG) performance status, hematology and serum/plasma chemistry, urinalysis, physical examination, vital signs measurements, radiologic assessment by computed tomography (CT) or magnetic resonance imaging (MRI). Patients will be required to provide a sample of the most recent archival tumor tissue. If an archival sample is not available, a screening biopsy must be obtained, unless the biopsy location is inaccessible, or the procedure is deemed unsafe by the investigator. The sample will be used for central laboratory confirmation of the mutations; however, receipt of archival tissue or central laboratory results are not required prior to patient starting on study. Data from procedures that are considered standard of care and performed before obtaining patient informed consent for the study may be collected and entered into the electronic case report form (eCRF).

3.1.2 Enrollment

Eligible patients will be enrolled in parallel in either Cohort A or Cohort B at all sites.

3.1.3 Treatment Period

Treatment cycles will be 28 days in length. All patients will be monitored for efficacy as well as safety throughout the treatment phase. Assessments will include, but may not be limited

to, physical examination, vital signs and weight measurement, hematology, serum chemistry, urinalysis, concomitant medications, ECOG performance status, disease status assessment, 12-lead ECG, AEs with any associated therapies and procedures, study drug administration and accountability. Blood samples will also be collected for PK and biomarker analyses.

Disease response to drug will be evaluated by physical examination and imaging methods, with tumor scans being done every 8 weeks of treatment (2 treatment cycles, \pm 7 days permitted). All responses (CR or PR) must be confirmed with a scan no less than 4 weeks after the initial response.

Disease progression will be determined by RECIST v1.1 ([Appendix 2](#)), or in the case of prostate cancer, by modified RECIST v1.1/PCWG3 guidelines ([Appendix 3](#)). If the radiologic assessment does not confirm disease progression, patients should continue on treatment and be assessed by RECIST v1.1 per the Schedule of Assessments. Patients experiencing disease progression by RECIST v1.1, as assessed by the investigator, will be discontinued from study treatment and enter follow-up. However, if the patient has met criteria for radiologic progression by RECIST, but the patient is still receiving benefit from the study drug(s) (eg, patient has mixed radiologic response or is continuing to have symptomatic benefit), according to the investigator, the decision to continue will be made jointly between the investigator and the sponsor (or designee), and the patient must consent prior to continuing treatment with rucaparib.

3.1.4 Post-treatment Period

Upon treatment discontinuation, regardless of reason (with the exception of withdrawal of consent or death), patients will have an End-of-Treatment (EOT) Visit with assessments as detailed in [Section 7](#).

All patients will be followed for at least 28 days after the last dose of study drug and will then proceed to long-term follow-up (LTFU).

Patients who discontinue treatment for a reason other than disease progression or death should continue to have tumor scans performed at the interval specified until radiological disease progression as assessed by the investigator, death, loss to follow-up, withdrawal from study, study termination, or initiation of subsequent anticancer treatments.

Ongoing serious adverse events (SAEs), AESIs and treatment-related CTCAE Grade 3/4 AEs will be followed until resolution or stabilization has been determined, death, or loss to follow-up. After the 28-Day Follow-Up Visit, only SAEs considered as potentially related to study drug should be reported per Clovis PV requirements and captured in the Clovis Pharmacovigilance (PV) database. This includes serious reports of pneumonitis or similar events, if considered to be related to study drug.

After the 28-day Safety Follow-up Visit, AESIs of MDS and AML, irrespective of causality, should be reported per Clovis PV requirements and captured in the Clovis PV database. AESIs of pneumonitis or similar events should only be reported up to, but not beyond, the 28-day Safety Follow-up Visit.

All patients will be followed for survival and subsequent treatments every 12 weeks (\pm 14 days) relative to the last dose of rucaparib until death, loss to follow-up, withdrawal of consent or study closure.

An optional tumor biopsy will be collected from patients who experience disease progression and provide additional consent.

If a patient begins subsequent anticancer therapy, the sponsor will terminate collection of SAEs, with the exception of the AESIs of MDS and AML.

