Abbreviations: AE = adverse event; AESI = adverse event of special interest; BRCA = breast cancer gene; ctDNA = circulating tumor deoxyribonucleic acid; ECG = electrocardiogram; ECOG = Eastern Cooperative Oncology Group; gBRCA = germline BRCA; HRD = homologous recombination deficiency; PK = pharmacokinetics; PSA = prostate-specific antigen; RECIST = Response Evaluation Criteria in Solid Tumors; SAE = serious adverse event; sBRCA = somatic BRCA; WOCBP = women of child-bearing potential.

- a The study visit window in the treatment phase is ± 3 days, unless noted otherwise for a particular assessment. Study visits should take into account the subjects investigational product supply. Only 1 cycle of oral study drug will be dispensed to the subject on Day 1 of each cycle.
- b Follow-up visit should occur 28 days (±7) from the last dose of study drug, or can be performed on the date of discontinuation if that date is at least 28 days from last dose. Chemistry and hematology are only necessary at follow-up visit if toxicities are present. The follow-up visit should be conducted in person.
- c Informed consent may be completed outside the screening window of 28 days prior to study start, as informed consent does not expire, except as required by applicable regulatory requirements or if informed consent is withdrawn by patient.
- d All patients will be required to provide adequate tumor tissue (tumor content > 30% is strongly preferred) for analysis. In the event archival tumor tissue is not available, a screening biopsy sample must be collected and provided to the central laboratory, unless the biopsy procedure is considered unsafe by the investigator or the biopsy site is considered inaccessible. Availability of adequate tumor tissue samples must be confirmed prior to enrollment, but tissue sample may be sent after the patient is enrolled. Submission of a tumor block is strongly preferred. Refer to the Laboratory Manual for detailed sample collection and handling instructions.

- e Height measured at screening and at the EOT visit only.
- f 12-lead ECGs may be repeated at other times as clinically indicated.

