- ^m **First dose of study drug in Cycle 1 should be administered within 3 days of enrollment.** Study treatment continues in 28-day cycles until disease progression, unacceptable toxicity, patient or physician request to discontinue, death, initiation of any other cancer therapy, positive pregnancy test, or termination of the study. Study visit should take into account the patient's rucaparib supply. A quantity of rucaparib sufficient to complete 1 cycle (28 days) should be dispensed to the subject/patient on Day 1 of each cycle.
- ⁿ AEs, SAEs, and AESIs that occur after first administration of study drug through to 28 days after last dose of study drug(s). In addition, SAEs that were related to a screening procedure will also be recorded. Ongoing SAEs, AESIs, or treatment-related Grade 3/4 AEs will be followed to resolution or stabilization. After the Safety Follow-up Visit, only SAEs considered as potentially related to study drug (including serious reports of pneumonitis or similar events, ie, interstitial lung disease, pulmonary fibrosis, acute interstitial pneumonitis, alveolitis, hypersensitivity pneumonitis, and organizing pneumonia, if considered to be related to study drug), and the AESIs of MDS and AML regardless of causality, will be recorded in the eCRF. If a patient discontinues from treatment in the rollover study and begins a subsequent anticancer therapy, the sponsor will terminate collection of SAEs.
- ^o Cycles 2 through 6 only. PK samples should be collected prior to the morning dose on the visit days, and as close as possible to 12 hours after the last dose (even if the morning dose on the specified visit days is not administered). If a new treatment cycle is delayed, the predose PK sample closest to 12 hours after the last dose should still be collected on that visit and should not be collected on Day 1 of the delayed treatment cycle. Refer to the Laboratory Manual for detailed sample collection and handling instructions.

- p An optional tumor biopsy may be collected from patients within 30 days after the time of disease progression or treatment discontinuation. Additional consent is required. Refer to the Laboratory Manual for detailed sample collection and handling instructions.

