8.6 Pregnancy or Drug Exposure during Pregnancy

If a patient becomes pregnant during the study, rucaparib should be held immediately.

A pregnancy is not considered to be an AE or SAE; however, any pregnancy occurring in a study patient or partner of a male study patient during study participation or within 6 months of the last dose for female patients, and within 3 months of the last dose for partners of male study patients, must be reported to the sponsor using the Pregnancy Report Form within the same timelines as an SAE.

All pregnancies are to be followed through to outcome, if possible. Once the outcome of the pregnancy is known, the Pregnancy Outcome Report Form is to be completed and reported to the sponsor.

AEs, SAEs, or AESIs that occur during pregnancy will be assessed and processed according to the AE or SAE/AESI processes using the appropriate AE or SAE/AESI forms.

If any female partner becomes pregnant by a male study patient while he is receiving rucaparib, or within 3 months after the last dose of rucaparib, she will be asked to provide optional consent to allow follow-up until final outcome/delivery to determine if rucaparib has any effect on the pregnancy and fetal development.

8.7 Recording of Adverse Events, Serious Adverse Events, and Adverse Events of Special Interest

Events that occur after signing the ICF but prior to initiation of rucaparib, unless due to a protocol-mandated procedure, are to be recorded on the Medical History eCRF; however, events are to be reported as SAEs if serious and related to a protocol-mandated procedure during this time. Any AE that occurs after first dose of rucaparib through 28 days after receiving the last dose of rucaparib is to be recorded on the AE eCRF.

After the 28-day reporting window after discontinuation of treatment, only SAEs assessed as potentially related to rucaparib should be reported per Clovis PV requirements and captured in the Clovis PV database. This includes serious reports of pneumonitis or similar events, ie, interstitial lung disease, pulmonary fibrosis, acute interstitial pneumonitis, alveolitis necrotizing, alveolitis, hypersensitivity pneumonitis, and organizing pneumonia, if considered to be related to study drug.

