After the 28-day Safety Follow-up Visit, AESIs of MDS and AML, irrespective of causality, should be reported per Clovis PV requirements and captured in the Clovis PV database. AESIs of pneumonitis or similar events should only be reported up to, but not beyond, the 28-day Safety Follow-up Visit.

Information on the follow-up of AEs, SAEs, and AESIs is provided in [Section 8.8](#).

In order to avoid vague, ambiguous, or colloquial expressions, the AE should be recorded in standard medical terminology rather than the patient's own words. Whenever possible, the investigator should combine signs and symptoms that constitute a single disease entity or syndrome into a final diagnosis, if appropriate. For example, fever, cough, and shortness of breath may be reported as pneumonia, if that is a reasonable diagnosis.

Each AE is to be evaluated for **causal relationship** to the investigational drug, severity, and seriousness. The action taken and the outcome must also be recorded.

SAEs and AESIs that occur during the study or within 28 days after receiving the last dose of rucaparib, whether or not related to rucaparib, must be reported immediately (ie, **within 24 hours** of knowledge of the event or additional information for a previously-reported event) to the sponsor/SAE designee. The contact information for reporting of SAEs/AESIs can be found on the SAE/AESI Reporting Form.

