9.7.2 Adverse Events

Adverse events will be classified using the Medical Dictionary for Regulatory Activities (MedDRA) classification system. The severity of the toxicities will be graded according to the NCI CTCAE v5.0 or later TEAEs are defined as AEs with onset date on or after the date of first dose of study drug until 28 days after the last dose of study drug.

The number and percentage of patients who experienced TEAEs for each system organ class (SOC) and preferred term will be presented. Multiple instances of the TEAE in each SOC and multiple occurrences of the same preferred term are counted only once per patient. The number and percentage of patients with at least one TEAE will also be summarized.

Separate tables will be presented as follows:

- All TEAEs;
- TEAEs by CTCAE grade;
- Grade 3 or greater TEAEs;
- Treatment-related TEAEs
- Serious TEAEs;
- Treatment-related serious TEAEs;
- TEAEs with an outcome of death;
- TEAEs leading to discontinuation of study;
- TEAEs resulting in interruption/delay of study drug; and TEAEs resulting in dose reduction of study drug.

The incidence of TEAEs will be summarized by relationship to study drug (rucaparib) according to the following categories: “treatment-related,” or “not treatment-related”. If a patient experiences multiple occurrence of the same AE, with different relationship categories for the study drug, the patient will be counted once, as a relationship category of treatment related.

If a patient experiences multiple occurrence of the same AE with different toxicity grades, the patient will be counted once for the maximum (most severe) toxicity grade. AEs with a missing toxicity grade will be presented in the summary table with a toxicity grade of “Missing.” For each toxicity grade, the number and percentage of patients with at least 1 TEAE of the given grade will be summarized.

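### Two cut-off rules, the Safety Follow-up Visit and the start of new therapy, conflict with the 28-day AE/SAE collection window that the TEAE tables rely on

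*Combined protocol and SAP*

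**What the plan says.** **Day 28, any causality.** Section 8.7 states: "Any AE that occurs after first dose of rucaparib through 28 days after receiving the last dose of rucaparib is to be recorded". It also requires prompt reporting of "SAEs and AESIs that occur during the study or within 28 days after receiving the last dose of rucaparib, whether or not related to rucaparib". Section 7.3.4.1 and the first sentence of Table 5 footnote n set the same end point. Section 8.2 treats any event resulting in death within that period as an SAE. Section 9.7.2 defines TEAEs in these terms: "AEs with onset date on or after the date of first dose of study drug until 28 days after the last dose of study drug", with no earlier cut-off at a visit or at new therapy.

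**The visit.** Section 3.1.4 states: "After the 28-Day Follow-Up Visit, only SAEs considered as potentially related to study drug should be reported". A later sentence of footnote n does the same, keeping MDS and AML. Sections 3.1.4 and 8.7 both end reporting of pneumonitis AESIs at the visit. Footnote b sets its timing: "Follow-up visit should occur 28 days (±7) from the last dose of study drug".

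**Next anticancer therapy.** The closing sentence of Section 3.1.4 reads: "If a patient begins subsequent anticancer therapy, the sponsor will terminate collection of SAEs, with the exception of the AESIs of MDS and AML". The counterpart in footnote n reads: "If a patient discontinues from treatment in the rollover study and begins a subsequent anticancer therapy, the sponsor will terminate collection of SAEs".

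**The concern.** A site can comply with one of these rules while breaching another. The tables of serious TEAEs and of TEAEs with an outcome of death in Section 9.7.2 assume complete collection to day 28. A site that applies the therapy cut-off or the visit cut-off literally would leave out some events belonging in those tables, while a site that applies Section 8.7 would include them.

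The therapy cut-off names SAEs and does not name non-serious AEs. Read literally, the more serious events would be followed for a shorter time than the less serious ones. Any loss under this rule would fall on patients who start another treatment soon after rucaparib, so it would not be random.

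The visit cut-off matters for pneumonitis as well. Section 1.1.7.1 says it was made an AESI to gather data for a thorough evaluation. On days 22 to 28 one sentence of Section 8.7 requires such an event to be reported and, if the visit has already taken place, another says not to report it.

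**Working it through.** The plan states no figure for lost events, so there is none to reproduce. The check sets the passages side by side and counts days.

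**1. Reference window.** Collection and the TEAE definition both end on day 28 after the last dose (Sections 7.3.4.1, 8.2, 8.7, 9.7.2; first sentence of footnote n).

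**2. Visit rule.** Footnote b gives 28 ± 7 days, so the earliest visit is 28 − 7 = day 21 and the latest 28 + 7 = day 35. For a visit on day v, the gap is max(0, 28 − v).
- v = 21: gap = 7 days (days 22 to 28).
- v = 28 or later: gap = 0.

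The 7 days are 7/28 = 25% of the post-dose period only. The TEAE window also includes treatment time T, so the share of the whole window is 7/(T + 28). With T assumed to be one 28-day cycle, this is 7/56 = 12.5%. With T assumed to be six cycles (168 days), it is 7/196 = 3.6%.

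In the gap, the visit rule leaves out unrelated SAEs and any pneumonitis AESI that is not a related serious event. Potentially related SAEs, MDS and AML remain reportable.

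**3. New-therapy rule.** If therapy starts on day d < 28, SAE collection ends for the remaining 28 − d days, with only MDS/AML excepted, so related SAEs are included in the loss. For assumed values of d:

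| d | Days of SAE collection lost |
|---|---|
| 7 | 21 |
| 14 | 14 |
| 21 | 7 |

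Nothing in the text rules out d < 28. The synopsis bars other anticancer therapy only while the patient is receiving rucaparib. Section 6.2 bars it during study participation, but Section 3.1.4 and footnote q record subsequent treatments during follow-up, so Section 6.2 does not secure a 28-day gap.

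**4. Footnote n.** Its termination sentence lacks the MDS/AML exception of Section 3.1.4 and depends on a rollover study that the supplied text does not otherwise describe. The sentence just before it keeps MDS/AML regardless of causality, as do Sections 3.1.4, 8.7 and 8.8, and the long-term follow-up row of Table 5 lists AESIs.

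**5. Comparison within the plan.** Sections 9.7.3 and 9.7.4 end the laboratory and vital-sign periods at day 28 or the last Safety Follow-up Visit, whichever is later. The plan therefore allows there for the two dates to differ. The AE rules contain no such provision.

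**6. What cannot be computed.** The documents give no distribution of visit days, no rate of early next therapy and no SAE rate. The number of events lost is unknown and could be zero.

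**The case against.** The strongest reply is that day 28 is the controlling rule. It is stated many times, including at the start of footnote n itself. Section 8.7 ties the general switch to related-only SAEs to the 28-day reporting window, and Sections 7.3.4.1 and 8.8 use similar wording. Section 3.1.4 says patients are followed for at least 28 days. On this view, references to the 28-day visit are shorthand for the window. The therapy sentence, placed after the long-term follow-up text, would be meant only to close the open-ended collection after day 28.

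That reading is reasonable, and many sites would probably follow it. It is still an inference: the therapy sentence carries no such limit, and a visit permitted from day 21 is not the same as day 28.

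The objection does defeat several stronger conclusions that a reader might draw:
- **Sites will stop collecting on day 21.** A site would have to disregard Section 8.7 and the first sentence of footnote n.
- **MDS/AML reporting is lost.** The surrounding provisions keep it, and the footnote sentence depends on a study that is not described here.
- **A quarter or a half of the window is lost.** Such shares count post-dose days only, whereas the TEAE window starts at the first dose.
- **Early switching is shown by the entry washout in exclusion criterion 7.** That criterion concerns therapy before rucaparib and says nothing about timing afterwards.
- **Deaths go unrecorded.** Survival follow-up captures the death; what may be missing is its reporting as an SAE. Section 8.4 already excludes events clearly related to progression from AE and SAE reporting.

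**Conclusion.** The conflict is real and should be corrected. Its established size is up to 7 post-dose days under the visit rule, for unrelated SAEs and for pneumonitis AESIs that are not related serious events. Under the therapy rule it is 28 − d days for all SAEs except MDS/AML. Both figures assume that sites apply the conflicting sentences literally, and the second also needs a patient to start new therapy before day 28. The documents do not show how often either occurs, so they do not support a claim that the reported rates of serious TEAEs will be understated by any particular amount. The footnote n discrepancy on MDS/AML is a wording conflict, not a demonstrated loss of follow-up.

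**What to change.** Reconcile the passages by amendment:
- In Sections 3.1.4 and 8.7 and in footnote n, state that all AEs, SAEs and AESIs, including pneumonitis, are collected through day 28 after the last dose, regardless of the visit date or the start of new therapy.
- State that the restriction to related SAEs and the new-therapy cut-off apply only after day 28.
- In the termination sentence of footnote n, delete the reference to the rollover study and add the MDS/AML exception from Section 3.1.4.

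The visit window in footnote b can stay as it is. The cost is a wording change. The small downside is that some SAEs inside the window will be confounded by the new therapy; these can be flagged from the subsequent-treatment data already collected.
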